### 2.8.4.2 Vital signs

Assessed vital signs include:

- systolic/diastolic blood pressure
- pulse rate
- temperature

Patient's values on blood pressure and pulse rate will be calculated as a mean of three readings. Readings with missing values will be ignored.

Descriptive summary statistics presented by type of measurement and treatment group will contain vital signs measurements for each study visit as well as change from baseline.

### 2.8.4.3 Columbia Suicide Severity Rating Scale (C-SSRS)

The number and percentage of subjects reporting any suicidal ideation or any suicidal behavior will be summarized descriptively by treatment group and by visit, for DBTE and for safety follow-up period, respectively.

Shift table of C-SSRS maximum severity of suicidal ideation/behavior compared to baseline will be provided by treatment group for DBTE and for safety follow-up period, respectively.

No statistical testing will be performed on C-SSRS.

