5.6.5 Early study termination by the sponsor

The study can be terminated by Novartis at any time for any reason. This may include reasons related to the benefit-risk assessment of participating in the study, practical reasons, or for regulatory or medical reasons (including slow enrollment). Should this be necessary, the patient must be seen as soon as possible and treated as a prematurely withdrawn patient. The investigator may be informed of additional procedures to be followed in order to ensure that adequate consideration is given to the protection of the patient's interests. The investigator will be responsible for informing the Institutional Review Board / Independent Ethics Committee (IRBs/IECs) of the early termination of the trial.

6 Visit schedule and assessments

Table 6-1 and Table 6-2 list all of the assessments and indicate with an "X" when the visits are performed.

Patients must be seen for all visits on the designated day, or as close to it as possible. Missed or rescheduled visits should not lead to automatic discontinuation.

During visits 102 to visit 107, intervals between visits must not exceed 7 +/- 1 day calculated from Visit 101 (Day1), to ensure continuous supply regarding oral medication.

During visits 108 to visit 199, intervals between visits should not exceed 28 +/- 4 days calculated from Visit 101 (Day 1). If the visit has to be scheduled outside this window, an approval from the sponsor has to be collected to ensure continuous supply of oral medication and patient safety regarding s.c. medication.

	Screen	Baseline	Double – Blind Treatment Epoch (Titration)						Double – Blind Treatment Epoch (Maintenance)						Follow Up ²
Visit number ¹	0	1	101	102	103	104	105	106	107	108	109	110	111	199	201
End of Week	-6	-4	0	1	2	3	4	5	6	8	12	16	20	24	28
Day	-42	-28	1	8	15	22	29	36	43	57	85	113	141	169	197
Baseline Phase Completion form		x													
Double-Blind Treatment Phase Completion form														x	
Follow-Up Phase Completion form															x

- 1 – All study visit target dates are to be calculated from the Day 1 visit date and all study procedures for a given visit should be completed on the same day.
- 2 – The Follow-Up Visit is required 8 weeks after last IMP injection (erenumab / corresponding Placebo) for patients who discontinue the study or 4 weeks after V199 for patients who complete the study. The Follow-Up visit can be skipped if any other safety follow up visit occurred 8 weeks after last IMP injection.

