- 3 – Including prior prophylactic medication.
- 4 – Includes blood pressure, pulse and temperature.
- 5 – Patient brings to each visit for use at site
- 6 – To be completed during applicable study visits before study drug administration, where applicable.
- 7 – Should also be performed at unscheduled visits.
- 8 – SAEs will be collected after signing of the informed consent through the end of the Follow-Up Epoch (8 weeks after the last IMP injection). Non-serious AEs will be collected after randomization (Visit 101) through the end of the Follow-Up Epoch (8 weeks after the last IMP injection).
- 9 – Study drug is administered by study staff, during the applicable study visits, q.m., s.c..
- 10 – Oral study drug will be dispensed to the patient at the center during the applicable study visit for home application.
- 11 – Sites will access the Interactive Response Technology (IRT) System to register study early termination.
- 12 – Should be additionally performed at any visit if deemed necessary by the investigator due to AEs.
- 13 – Should be performed/registered by the investigator prior to dosing during DBTE.
- TD = Treatment discontinuation; PFS = Prefilled syringe; PSD = Premature subject discontinuation; X = Assessment to be recorded in the source documents and the clinical data base; S = Assessment to be recorded as source documentation only.

Table 6-2 Abbreviated schedule of assessments (ASA) for patients with Treatment Discontinuation (TD)

Visit number	V105-ASA	V108-ASA	V109-ASA	V110-ASA	V111-ASA	V199-ASA	V201-ASA ²
End of Week¹	4	8	12	16	20	24	28
Complete Physical Exam						S	
Brief Physical Exam	S	S	S	S	S		
Weight						X	X
Vital Signs ³	X	X	X	X	X	X	X
Chemistry/Hematology ¹²		X				X	X
Serum Pregnancy						X	
Urine pregnancy	S	S	S	S	S		X
ECG						X	
Clinical Outcomes (eDiary)	eDiary should be maintained						
SF-36 ⁴ (eDiary)	X	X	X	X	X	X	
HIT-6 ⁴ (eDiary)	X	X	X	X	X	X	
C-SSRS	X	X	X	X	X	X	
Concomitant Medications	X	X	X	X	X	X	X
Adverse Events ⁵	X	X	X	X	X	X	X
Serious Adverse Events ⁵	X	X	X	X	X	X	X
Follow Up Phase Completion form							X

1 – All study visit target dates are to be calculated from the Day 1 visit date, and all study procedures for a given visit should be completed in the same day.

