7.6 Prospective suicidality assessment

The Columbia-Suicide Severity Rating Scale (C-SSRS) is a questionnaire that prospectively assesses Suicidal Ideation and Suicidal Behavior (Posner 2011). The C-SSRS must be administered at each visit, including unscheduled visits.

A validated version of the C-SSRS will be used to capture self-reported C-SSRS data via web-based interactive response system (eC-SSRS). The eC-SSRS uses a detailed branched logic algorithm to perform the C-SSRS patient interview, evaluating each patient’s suicidality ideation and behavior in a consistent manner. At the conclusion of each assessment, the investigator will receive a detailed eC-SSRS Findings Report via e-mail or fax. If the system

assesses the patient as having positive suicidal signs, the investigator will be immediately notified by either fax, e-mail and/or via telephone.

If, at any time after screening and/or baseline, the score is “yes” on item 4 or item 5 of the Suicidal Ideation section of the C-SSRS or “yes” on any item of the Suicidal Behavior section, the patient must be referred to a mental health care professional for further assessment and/or treatment. The decision on whether the study treatment should be discontinued is to be taken by the investigator in consultation with the mental health professional to whom the patient is referred.

In addition, all life-threatening events must be reported as SAEs. For example, if a patient answers “yes” to one of the questions in the Suicidal Behavior section, an SAE must be reported if the event was life-threatening. All events of “Non-Suicidal Self-Injurious Behavior” (question also included in the Suicidal Behavior section) should be reported as AEs and assigned the appropriate severity grade.

All SAEs relating to suicidal behavior must be reviewed by the Safety Management Team or early project teams.

8 Data review and database management

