**Table 2.1.1.2-1. Study Visit Windows in the DBTE**

Study visit	Target day	Study Day
Week 0	1	1
Week 1	8	2 - 11
Week 2	15	12 - 18
Week 3	22	19 - 25
Week 4	29	26 - 32
Week 5	36	33 - 39
Week 6	43	40 - 49
Week 8	57	50 - 70
Week 12	85	71 - 98
Week 16	113	99 - 126
Week 20	141	127 - 154
Week 24	169	155 - 182

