#### **Suicidal behavior**

- Cat. 6 - Actual attempt (non-fatal)
- Cat. 7 - Interrupted attempt
- Cat. 8 – Aborted or self-interrupted attempt
- Cat. 9 - Preparatory acts or behavior
- Cat. 10 - Suicide

The C-SSRS is administered at each visit, including unscheduled visits. Two versions depending on the type of visits will be used in this study: Screening and Since Last Visit. Please refer to [C-SSRS scoring](#) for scoring details.

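### By-visit C-SSRS percentages mix look-backs of 7, 14 and 28 days, so they cannot be compared across visits and, once patients stop treatment, not always within a visit

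*SAP*

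**What the plan says.** SAP 2.8.4.3 plans two C-SSRS outputs for the double-blind treatment epoch (DBTE) and tests neither. The first is by visit: "The number and percentage of subjects reporting any suicidal ideation or any suicidal behavior will be summarized descriptively by treatment group and by visit". The second is a shift table of maximum severity against baseline, by treatment group, over the whole DBTE.

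On the instrument, the C-SSRS part of SAP 2.1.1.5 says: "Two versions depending on the type of visits will be used in this study: Screening and Since Last Visit". Protocol 7.6 sets the frequency: "The C-SSRS must be administered at each visit, including unscheduled visits".

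On timing, Protocol Section 6 says: "During visits 102 to visit 107, intervals between visits must not exceed 7 +/- 1 day". From Visit 108 the spacing is 28 days with a 4-day tolerance, counted from Day 1. SAP Table 2.1.1.2-1 gives the target days and mapping windows; its Week 12 line, for example, reads "Week 12 85 71 - 98" (week, target day, window). SAP 2.1.1.2 maps C-SSRS reports to the nearest of these windows.

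Patients who stop study treatment leave this schedule. Under Protocol 5.6.2 and Table 6-2 they are seen at Weeks 4, 8, 12, 16, 20 and 24, with a C-SSRS at each.

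**The concern.** A form that asks about the time since the last visit measures what happened over that interval. When intervals differ, the percentages are period figures over unequal periods, and the SAP sets them side by side with no scaling and no note.

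The short intervals coincide with topiramate titration and the long ones with most of maintenance. A reader looking for a change in suicidality between the two phases would see a step upwards even if risk had not changed. Protocol 3.6 lists mood problems among the commonly reported adverse events of topiramate, so this contrast will be examined.

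The abbreviated schedule adds a second difficulty. In one row, a patient who has stopped treatment may be reporting over a longer interval than a patient still on treatment. The trial's primary hypothesis concerns a difference between arms in AE-related stopping, so an imbalance in such patients is a realistic prospect.

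**Working it through.** **Inputs.** Target days 1, 8, 15, 22, 29, 36, 43, 57, 85, 113, 141 and 169 (Protocol Section 6; SAP Table 2.1.1.2-1). Administration at every visit (Protocol 7.6). The documents give no C-SSRS rate or episode length, so there is no figure to reproduce; rates and durations below are assumptions.

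**Step 1: look-back on the full schedule**, as the difference between consecutive target days.

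- Weeks 1-6: 8-1, 15-8, 22-15, 29-22, 36-29, 43-36 = 7 days each
- Week 8: 57-43 = 14 days
- Weeks 12, 16, 20, 24: 85-57, 113-85, 141-113, 169-141 = 28 days each

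**Step 2: constant risk, brief independent events.** P(L) = 1 - exp(-λL), with λ = -ln(1 - P28)/28. For an assumed P28 of 2%, λ = 0.0202/28 per day, which gives P(7) = 0.50%, P(14) = 1.01% and P(28) = 2.00%. The 28-day to 7-day ratio is 3.97. Over other assumed 28-day rates it is 4.00 (0.1%), 3.85 (10%) and 3.69 (20%).

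**Step 3: constant risk, ideation that persists.** Let ideation be a state with onset rate a and mean duration D days. Then P(L) = 1 - (1 - π)exp(-aL), with π = a/(a + 1/D). For rare events the 28-day to 7-day ratio is close to (D + 28)/(D + 7). With P28 held at 2%:

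| Mean episode (days) | Week 1-6 visit | Week 8 | Week 12-24 visit | Ratio 28/7 |
|---|---|---|---|---|
| 1 | 0.56% | 1.04% | 2.00% | 3.60 |
| 7 | 0.80% | 1.20% | 2.00% | 2.49 |
| 14 | 1.00% | 1.34% | 2.00% | 1.99 |
| 28 | 1.25% | 1.50% | 2.00% | 1.60 |
| 168 | 1.79% | 1.86% | 2.00% | 1.12 |

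The ratio is above 1 in every case and never exceeds 4.

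**Step 4: look-back after stopping treatment.** Take a patient on 25 mg who stops at the Day 8 visit. Protocol 5.5.4 requires no taper at that dose, so no post-taper visit follows. The next scheduled C-SSRS is at Week 4: 29-8 = 21 days, against 29-22 = 7 days for an on-treatment patient in the same row.

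**Step 5: possible effect on the arm comparison.** If a fraction d of the assessed patients has the longer look-back, the mean look-back at Week 4 is 7(1-d) + 21d. The fractions are assumptions.

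- 5% vs 10%: 7.70 vs 8.40 days, ratio 1.09
- 10% vs 40%: 8.40 vs 12.60 days, ratio 1.50

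With the longest possible gap of 28 days in place of 21, the Week 4 ratios are 9.10/8.05 = 1.13 and 15.40/9.10 = 1.69. At Week 8, 28 days against 14 gives 15.40/14.70 = 1.05 and 19.60/15.40 = 1.27. For brief events the expected percentages scale in roughly the same way; for persistent ideation the effect is smaller.

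**Step 6: equal blocks.** Weeks 1-4 cover 4 × 7 = 28 days, Weeks 5-8 cover 7 + 7 + 14 = 28 days, and each later visit covers 28 days. Under the Step 2 assumption every block reads 2.00%.

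**The case against.** The strongest reply is that this is an untested descriptive table with a companion that avoids the problem. The maximum-severity shift table pools all DBTE visits by arm and has no 7/14/28-day step. The SAP defines a positive answer for a specific visit, does not call the percentages rates, and plans no comparison between visits. Care of individual patients runs through immediate notification and referral under Protocol 7.6, not through this table. All of this stands and limits the severity. However, the shift table has no time dimension, so it cannot correct a misread time pattern.

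A reader might infer that a four-fold rise is built into the table. The documents do not support that. Four-fold needs constant risk, brief independent events and full recall, and Step 3 shows how quickly the ratio falls when ideation persists.

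A reader might also infer that every early stopper has a longer look-back and is missing from the weekly rows. That goes too far. Under Protocol 5.6.2, patients who took 75 or 100 mg for at least a week taper for one week and then have an unscheduled visit, at which Protocol 7.6 requires a C-SSRS. On the example titration scheme a patient stopping on Day 36 is on 100 mg. The post-taper visit falls near Day 43 and would map to Week 6, leaving 57-43 = 14 days at Week 8, the same as on treatment. A stop at the Day 22 visit gives 29-22 = 7 days at Week 4, again no difference. In the other direction, a patient already off treatment who attends the Week 4 visit, with no unscheduled visit after it, has 28 days at Week 8.

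Finally, patients on the full schedule share the same look-backs in both arms, so for them the arm comparison at a given visit is not distorted.

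**Conclusion.** The point holds as one about descriptive safety reporting, of limited severity. On the full schedule the by-visit percentages cover 7, 14 and 28 days, and the SAP neither adjusts for this nor says so. They should not be read as a time course. Under constant risk the 28-day visits can read anywhere from just above 1 to four times the weekly ones, and nothing in the documents fixes a value within that range.

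The arm comparison is affected only through patients on the abbreviated schedule, mainly at Weeks 4 and 8, and only if their share differs by arm. The Step 5 ratios illustrate this under assumed shares and are not predictions. Unscheduled visits shorten the look-back wherever they occur.

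The C-SSRS row of Table 6-1 is not in the text available, so administration at every full-schedule visit rests on Protocol 7.6 and SAP 2.1.1.5.

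**What to change.** In SAP 2.8.4.3, add a table of subject incidence by equal four-week blocks built from the SAP's mapped visits: Weeks 1-4, Weeks 5-8, Week 12, Week 16, Week 20 and Week 24. Count a patient once per block if any report in it is positive, including reports from unscheduled visits. This fits the subject-incidence definition already in SAP 2.1.1.5. Show on-treatment and post-discontinuation reports in separate rows beneath a total, and say where a report spanning the stop date is counted. Only the total row covers an equal 28 days for everyone.

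Build the blocks from mapped visits and not from fixed day limits. A Week 8 report on Day 60 is within the 4-day tolerance but would fall into the next block if the cut were at Day 57. A Week 24 report on Day 172 would be lost if the last block ended at Day 169.

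Keep the by-visit table, which preserves the weekly detail during titration, and state in it the nominal look-back for each visit, noting that it can differ after treatment discontinuation or an unscheduled visit.

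The cost is one additional table and some SAP and shell wording; all the data are already collected. The blocks equalise the period covered but not the number of times a patient is asked, so a small difference could remain if recall over 28 days is incomplete.

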## 2.9 Pharmacokinetic endpoints

Not applicable.

## 2.10 PD and PK/PD analyses

Not applicable.

## 2.11 Patient-reported outcomes

Patient reported outcomes assessed in the study are limited to those used for exploratory efficacy analyses (MMD, HIT-6, SF-36v2, [REDACTED]), safety analyses (C-SSRS) and patient's baseline characteristics (BDI-II).

[REDACTED]

- [REDACTED]
- [REDACTED]

## 2.12 Biomarkers

Not applicable.

## 2.13 Other Exploratory analyses

[figure not shown]
See [Analysis of exploratory objectives](#). No additional exploratory variables are specified.

## 2.14 Interim analysis

No interim analyses is planned.

■ [REDACTED]

[REDACTED]

## 5 Appendix

### 5.1 Imputation rules

No imputation will be done for missing primary and exploratory endpoints. Subjects with missing response information on the secondary endpoint (achievement of at least 50% reduction from baseline in MMD over the last 3 months (month 4, 5, and 6) of the double-blind epoch) will be imputed as non-response.

#### 5.1.1 Study drug

#### 5.1.2 Concomitant medication date imputation

##### Incomplete day

Incomplete start day will be imputed as MAX(date of study day 1, *earliest possible start date*).  
Incomplete end day will be imputed as MIN(EoS, *latest possible end date*).

*Earliest possible start/end date* is calculated on the eCRF page and refers to the first day of the corresponding month. *Latest possible start/end date* is calculated on the eCRF page and refers to the last day of the corresponding month.

##### Incomplete day/month

Incomplete start day/month will be imputed as MAX(date of study day 1, 1st January of the year entered).

Incomplete end day/month will be imputed as MIN(EoS, 31th December of the year entered).

##### Incomplete day/month/year

Incomplete day/months/year will not be imputed.

#### Prior therapies date imputation

##### Incomplete day

Incomplete start day will be imputed as earliest possible start date.

Incomplete end day will be imputed as MIN (date of the day prior to study day 1, *latest possible end date*).

##### Incomplete day/month

Incomplete start day/month will be imputed as 1st January of the year entered.

Incomplete end day/month will be imputed as MIN(31th December of the year entered, date of the day prior to study day 1).

**Incomplete day/month/year**

Incomplete start date will be imputed as very early date

Incomplete end date will be imputed as a date of the day prior to study day 1.

**5.1.2.1 Post therapies date imputation**

Not applicable.

**5.1.2.2 Other imputations**

**5.1.2.2.1 eDiary data**

Missing eDiary data in the calculation of monthly measurements about patients' migraine and non-migraine headaches will be handled using the following method:

1. For **monthly intervals with  $\geq 14$  days of eDiary days** (including retrospective eDiary days) in each interval:

Monthly migraine days will be prorated to 28-day equivalents. Prorated result does not need to be rounded.

2. For **monthly intervals with  $< 14$  days of eDiary use** (including retrospective eDiary days), all monthly measurement will be set to missing.

Monthly Endpoint	Condition	Proration Method (does not need to be rounded)
Monthly migraine days	
If eDiary days in entire baseline or interval post baseline <math>\geq 14</math> (including retrospective eDiary days), then do proration;
 
Else monthly measurement is set to missing
 
[eDiary day is a day with all headache related questions completed retrospectively or not]
	
Number of observed migraine days * 28/ Number of information days in interval
 
[information day is an eDiary day or headache day]

**5.2 AEs coding/grading**

Adverse events are coded using the Medical dictionary for regulatory activities (MedDRA) terminology.

Severity of adverse events is graded by investigator (mild, moderate, severe) and reflected in the eCRF.

### **5.3 Laboratory parameters derivations**

Not applicable.

### **5.4 Statistical models**

#### **5.4.1 Primary analysis**

[figure not shown]
See [Analysis of the primary objective](#)

[figure not shown]
#### **5.4.2 Key secondary analysis**

[figure not shown]
See [Analysis of the secondary objective](#)

### **5.5 Rule of exclusion criteria of analysis sets**

Exclusion criteria of analysis sets are complementary to those used for corresponding analysis set definitions (see [Analysis sets](#)).

## 5.8 Appendix C: Patient-reported Outcome Scoring rules/Forms/Instruments

### 5.8.1 BDI-II scoring

Beck Depression Inventory II (BDI-II) consists of 21 items, each with 4 or 6 response options.

#### *Missing data*

If more than 2 items have missing values, the total BDI score will be missing. If one or two items are missing, their score can be imputed with the mean of the non-missing scores before summing.

Items should be rescored according following rules:

Item number	Item label in the data set	Original value	Rescored value
1 - 15, 17, 19 - 21		0	0
		1	1

			2	2
			3	3
16	BDI_161L		0	0
18	BDI_181L		1	1
			2	1
			3	2
			4	2
			5	3
			6	3

**Scoring**

A single score is calculated by adding up the rescored values of 21 items. The range of values is 0 - 63.

**5.8.2 HIT-6 scoring**

The Headache Impact Test (HIT-6) is as a global measure of adverse headache impact, which assesses headache severity in the previous month and change in a patient’s clinical status over a short period of time.

**Scoring**

HIT-6 score will be calculated by the HIT-6 license owner “Optum” and ranges from 36 to 78.

[figure not shown]
**Score categorization**

[figure not shown]
HIT-6 score can be categorized into 4 grades:

- ≤ 49: little or no impact (49 or less)
- 50 - 55: some impact
- 56 - 59: substantial impact
- 60 - 78: severe impact

**5.8.3 SF-36v2 scoring**

SF-36v2 scores (eight subscores and two component summary scores) will be calculated by the SF-36v2 license owner “Optum”.

### 5.8.5 C-SSRS scoring

The Columbia-Suicide Severity Rating Scale (C-SSRS) is a questionnaire that prospectively assesses Suicidal Ideation and Suicidal Behavior based on following categories:

#### Suicidal Ideation

- Cat. 1 - Wish to be dead
- Cat. 2 - Non-specific active suicidal thoughts
- Cat. 3 - Active suicidal ideation with any methods (not plan) without intent or act
- Cat. 4 - Active suicidal ideation with some intent to act, without specific plan
- Cat. 5 - Active suicidal ideation with specific plan and intent

#### Suicidal behavior

- Cat. 6 - Actual attempt (non-fatal)
- Cat. 7 - Interrupted attempt
- Cat. 8 – Aborted or self-interrupted attempt
- Cat. 9 - Preparatory acts or behavior
- Cat. 10 - Suicide

Any suicidal ideation is identified by answer “yes” to at least one of the 5 suicidal ideation categories (cat. 1-5) for specific visit.

Any suicidal behavior is identified by answer “yes” to at least one of the 5 suicidal behavior categories (cat. 6-10) for specific visit.

Any suicidal ideation or behavior is identified by answer “yes” to at least one of the 10 categories (cat. 1-10) for specific visit.

